	
The 4-fold increase rate, GMT and GMI of anti-SARS-CoV-2 neutralizing antibody in 28 days after 2 doses of immunization.
 
The GMT of anti-SARS-CoV-2 neutralizing antibody in 3rd month, 6th month, 9th month, and 12th month after 2 doses of immunization.
 
Safety endpoints
 
 • The incidence of any adverse reactions/events within 30 minutes after each dose of vaccine • The incidence of solicited adverse reactions/events within D0~7 and unsolicited adverse reactions/events within D8~21 days after first dose of vaccination. The incidence of solicited adverse reactions/events within D0 ~ 7 and unsolicited adverse reactions/events within D8~28 days after second dose of vaccination. • The incidence of serious adverse events (SAE) from the beginning of the first dose to 12 months after the whole course of immunization.

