4.7.3. Relationship between Adverse Events and Investigational Vaccines

Impossible: Adverse events occur due to other factors, and there is sufficient evidence to prove that adverse reactions/events are caused by other reasons and have nothing to do with vaccination.

Unlikely: The occurrence of adverse events may be caused by other factors, such as the clinical status of the subject, other treatments or accompanying drugs, which are inconsistent with the known adverse reactions of vaccination.

Possible: Adverse events are consistent with known investigational vaccine information, have a reasonable temporal sequence with vaccination, and/or have occurred for vaccination. There is also a causal relationship with the investigational vaccine, but it may also be related to other factors.

Likely: Adverse events are consistent with the known investigational vaccine information and have causal relationship with the investigational vaccine, and cannot be explained by other factors, such as the clinical condition of the subject, other treatments or concomitant medication.

Definite: Adverse events are consistent with the known investigational vaccine information and have a causal relationship with the investigational vaccine, and this relationship cannot be explained by other factors, such as the clinical status of the subject, other treatments or accompanying drugs. In addition, adverse events occurred repeatedly when the subjects used the investigational vaccine again.

5. Selection and Withdrawal of Subjects

The subjects must fulfill all eligibility criteria to be involved in this study. No exemptions from any in-/exclusion criteria will be allowed. If any deviation from eligibility is retrospectively detected for an already randomized subject, the investigator and sponsor must decide immediately whether it is safe to treat this subject further within the study.

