5.1.5 Criteria for clinical trial suspension or termination

When the incidence of grade 3 and above adverse reactions reaches 15% or above or a case of suspected and unexpected serious adverse reactions (SUSAR) occurs, the sponsor,

investigator, and ethics committee shall discuss whether there is a need to suspend or terminate the clinical trial.

6. Study Treatments

At present, there is no Inactivated SARS-CoV-2 vaccine on the market. In order to ensure the scientific evaluation of the vaccine, considering that the final product of this vaccine contains adjuvant, aluminum hydroxide adjuvant with the same dose is selected as placebo control.

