The same statistical methods as above are used to evaluate VEs against severe cases of COVID-19 and deaths accompanied by COVID-19.

(4) Immunogenicity analysis (FAS and PPS analysis):

Statistical description: The antibody titer should be logarithmically transformed. Minimum value, maximum value, median and quartile spacing, GMT and 95% CI should be shown.

Comparison of antibody levels before immunization: Logarithmic conversion was carried out on antibody titers, and two independent sample T tests (normal and homogeneous variance) or corrected T tests (normal but uneven variance) shall be used to compare the GMT of neutralizing antibodies against COVID-19 before immunization between the experimental and placebo groups with various ages.

Comparison of antibody levels after immunization:

- ✓ calculate the antibody 4-fold increase rate and 95% CI of anti-SARS-CoV-2 antibody in the experimental and placebo groups with various ages after immunization, and make superiority comparison. If the lower limit of 95% CI of antibody 4-fold increase rate is $\geq 10\%$, the superiority hypothesis is valid;
- ✓ calculate 95% CI of GMT ratio of anti-SARS-CoV-2 antibody in the experimental and placebo group after immunization. If the lower limit of 95% CI ratio is ≥ 1.1 , the superiority hypothesis is valid;
- ✓ calculate the GMI and 95% CI of anti-SARS-CoV-2 antibody in the experimental group after immunization.

(5) Safety analysis (SS analysis)

Describe the frequency and number and incidence of adverse reactions/events. If a subject manifest the same adverse reaction/events repeatedly, the description on this adverse reactions/events should indicate the most severity, the closest relationship with vaccination and the earliest starting time. However, in the list of adverse reactions/events, all adverse reactions/events will be listed.

Using χ^2 test or correct χ^2 test or Fishers exact test, the incidence of total adverse reactions, systemic adverse reactions, local adverse reactions and unexpected adverse reactions in the experimental and placebo groups within 30 minutes, 0-7 days and 8-28 days after inoculation of each dose were compared χ^2 test or correct χ^2 test or Fishers exact is used to compare the difference of SAE incidence rate between the experimental and placebo groups within 360 days after the whole inoculation. The rank sum of two independent samples is used to compare the average grade of adverse reactions in the experimental and placebo groups.

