In the analysis of adverse events/reactions stratified by symptoms and SAE, MedDRA coding is used to carry out comparative analysis of SOC level and PT level respectively.

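### The named between-arm tests of non-serious safety cover adverse reactions only, and the causality scale gives a new type of event no clear route to being called a reaction, so these tests lose sensitivity

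*Protocol*

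**What the plan says.** **Endpoints.** The synopsis defines the safety endpoints on reactions and events together, for example "The incidence of any adverse reactions/events within 30 minutes after each dose of vaccine". Section 4.4.3 does the same and also names unsolicited events in the later window after each dose.

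**Tests.** Section 9.3(5), repeated in the synopsis, first describes and lists adverse reactions/events. The chi-square or Fisher tests for the windows of 30 minutes, 0-7 days and 8-28 days then compare "the incidence of total adverse reactions, systemic adverse reactions, local adverse reactions and unexpected adverse reactions in the experimental and placebo groups". The rank-sum test is used to "compare the average grade of adverse reactions in the experimental and placebo groups". Two further comparisons are not confined to reactions. One is a test to "compare the difference of SAE incidence rate between the experimental and placebo groups within 360 days after the whole inoculation". The other is a MedDRA comparison at SOC and PT level, introduced with "In the analysis of adverse events/reactions stratified by symptoms and SAE", for which no test is named.

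**Causality scale.** In section 4.7.3, Likely reads "Adverse events are consistent with the known investigational vaccine information and have causal relationship with the investigational vaccine". Possible and Definite also open with agreement with known vaccine information. Unlikely covers events that may have another cause, "which are inconsistent with the known adverse reactions of vaccination".

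**Unexpected reactions.** Section 9.3(5) tests them. Section 5.1.5 calls for a discussion of suspension or termination when "a case of suspected and unexpected serious adverse reactions (SUSAR) occurs". Section 8.3 requires expedited reporting of such cases.

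**The concern.** In a randomised, blinded, placebo-controlled trial, the comparison of arms is itself the evidence on causation. If events must first be judged related one by one, that evidence is passed through individual opinion. If that opinion is tied to what is already known about the vaccine, the events most exposed to removal are the ones not yet known.

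Two things are at stake. The named incidence and grade tests do not match the endpoints they serve, since no overall between-arm test of non-serious events regardless of causality is stated. The scale in 4.7.3 also sits badly with the idea of an unexpected adverse reaction. Such an event is related to the vaccine but lies outside its known profile, and the three upper categories begin by asking that it fit that profile.

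**Working it through.** The protocol states no figure on this point, so there is none to reproduce. The check is a comparison of the sections, followed by an illustration of scale.

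**1. Which comparisons use which events (9.3(5))**

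| Comparison | Events covered | Test named |
|---|---|---|
| Incidence at 30 min, 0-7 d, 8-28 d | Adverse reactions (total, systemic, local, unexpected) | Chi-square / Fisher |
| Average grade | Adverse reactions | Rank sum |
| SAE incidence, 360 days | All SAEs | Chi-square / Fisher |
| SOC and PT level | Adverse events/reactions and SAE | None |

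Non-serious events not classed as reactions therefore appear only in the fourth row and in the descriptive tables and listings.

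**2. Where a new event falls on the scale (4.7.3)**

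- Likely and Definite require agreement with known vaccine information. Definite also requires recurrence on repeat vaccination.
- Possible opens with the same condition but joins its parts loosely, with an and/or.
- Unlikely combines a possible other cause with a poor fit to known reactions.

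An event outside the known profile fails the opening condition of all three upper categories. If another explanation is conceivable, it meets Unlikely. Its classification as unrelated is probable, not automatic.

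**3. Illustration of scale**

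Inputs: n = 15,000 per arm (section 9.4.1) and two-sided 0.05. The event rates p0 (placebo) and p1 (vaccine), and the share f of events classed as related, are assumptions, because the protocol gives none. With blinded assessment, f is taken as equal in both arms.

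Formula: SE = √{[f·p1(1 − f·p1) + f·p0(1 − f·p0)]/n}; z = f(p1 − p0)/SE; power ≈ Φ(z − 1.96).

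For p0 = 0.2%, p1 = 0.4%, f = 1: SE = √[(0.004×0.996 + 0.002×0.998)/15,000] = 0.000631; z = 0.002/0.000631 = 3.17; power = Φ(1.21) = 0.89.

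| f | Expected events, placebo v vaccine | z | Power, 0.2% v 0.4% | Power, 0.5% v 0.75% |
|---|---|---|---|---|
| 1 | 30 v 60 | 3.17 | 89% | 78% |
| 0.50 | 15 v 30 | 2.24 | 61% | 49% |
| 0.25 | 7.5 v 15 | 1.58 | 35% | 28% |
| 0.10 | 3 v 6 | 1.00 | 17% | 14% |

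(Counts and z are for 0.2% v 0.4%.) The ratio of rates stays at 2 in every row of that scenario, so the filter costs power and does not distort the ratio while f is equal in the arms.

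**The case against.** **A new harm does not drop out altogether.** A reader might infer from the wording of the tests that every between-arm comparison is limited to related events and that a new harm would go unseen. The documents do not support that. The SAE test has no causality filter, the SOC/PT comparison takes in adverse events/reactions, all events are described and listed, and section 8.5 lets the DSMB see AE/SAE data by arm. This stands.

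**Power does not have to fall to the type I error.** That limit is reached only if every excess event is classed unrelated. Section 4.7.3 does not force this: Unlikely also needs a possible other cause, and Possible has its loose and/or. This stands.

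**Reaction may not mean judged related.** The protocol never says which categories make an event a reaction, and it uses the word loosely: section 4.7.3 under Impossible, and the general grading table in 4.7.2, apply it to events of any cause. Reading reaction as judged related is the usual meaning but an inference. The ambiguity itself needs settling, because section 9.3(5) uses both terms within one paragraph.

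**SUSAR handling has its own rule.** Section 8.3 requires reporting where either party cannot exclude a relationship and sends doubtful SAE causality to an expert meeting, so reporting does not depend on 4.7.3 alone. This weakens the conflict with 5.1.5 and 8.3 but leaves the one with the 9.3(5) test of unexpected reactions.

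**This is a matter for the SAP.** Table details are. Here, though, the protocol itself states which events the tests cover, and that coverage is narrower than its endpoints.

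**Pooled totals dilute rare effects.** This is also true. The same excess of 0.2 points on an assumed 5% background (5.0% v 5.2%) gives SE = √[(0.05×0.95 + 0.052×0.948)/15,000] = 0.00254, z = 0.002/0.00254 = 0.79 and power of about 12%. The illustration therefore applies to an event type or narrow category at the stated rates, not to a large pooled total.

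**Conclusion.** The point holds in a limited form. The named incidence tests and the grade test cover adverse reactions, while the endpoints are adverse reactions/events. The causality scale makes it likely that a new non-serious event leaves those tests, and it gives unexpected adverse reactions no clear place. Serious events are unaffected in the SAE test, and non-serious events remain in a SOC/PT comparison without a named test.

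The size cannot be fixed from the documents. Under the assumed rates, power falls from about 89% to between 61% and 17% as the share classed as related falls from one half to one tenth. This rests on the usual meaning of adverse reaction, on equal attribution in the two blinded arms, and on event rates that are assumptions. It bears on safety sensitivity only, not on efficacy or on data collection. The change is worth making because it is nearly free.

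**What to change.** - In 9.3(5) and the synopsis, apply the same chi-square/Fisher and rank-sum comparisons to all adverse events regardless of causality (total, local, systemic, unsolicited), alongside the adverse-reaction tests. There is no need to demote the reaction tests.
- State which categories of 4.7.3 make an event an adverse reaction.
- Reconcile 4.7.3 with 5.1.5, 8.3 and 9.3(5), so that inconsistency with known vaccine information does not by itself remove an event from the related categories.

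The cost is protocol wording and one more set of tables from data already collected. The downside is more background events in the all-event comparison, which is a reason to keep both sets of tests.

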	
reactions in the experimental and placebo groups within 30 minutes, 0-7 days and 8-28 days after inoculation of each dose were compared χ^2 test or correct χ^2 test or Fishers exact is used to compare the difference of SAE incidence rate between the experimental and placebo groups within 360 days after the whole inoculation. The rank sum of two independent samples is used to compare the average grade of adverse reactions in the experimental and placebo groups.
 
In the analysis of adverse events/reactions stratified by symptoms and SAE, MedDRA coding is used to carry out comparative analysis of SOC level and PT level respectively .

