4.4.3. Safety Endpoint

The incidence of adverse reactions/events within 30 minutes after each dose of vaccination.

The incidence of solicited and unsolicited adverse reactions/events within D0 ~ 7, and unsolicited events and SAEs within D8 ~ 21/28 after each dose of vaccination.

The incidence of serious adverse events (SAE) from the first dose of vaccination to 12 months after the last dose of vaccination.

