5.1.3. Exclusion criteria for the second dose of vaccine

1. Patients with high fever (axillary temperature ≥ 39.0 °C) lasting for 3 days after the previous dose of vaccine and severe allergic reaction;
2. Serious adverse reactions with causal relationship with the previous dose of vaccine;
3. Reach the endpoint of the study;
4. Urine pregnancy test positive;
5. for the subjects newly identified or with newly occurred symptoms which does not meet the inclusion criteria for the first dose or meets the exclusion criteria for the first dose after the previous dose of vaccine is vaccinated, the investigator shall determine whether they should continue to participate in the trial;
6. Other reasons for exclusion that investigator believes.

If any of the following occurs during the trial, the relevant subjects are not required to stop the trial:

- Non-specific immunoglobulins were used during the study;
- Continuous oral or IV administration of steroid hormones for 14 days.

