6.6. Administration Route and Immunization Procedure

Administration route: lateral deltoid muscle of upper arm, intramuscular injection.

Immunization procedure: The subjects will complete 2 doses of vaccine on D0, D21(+7) days.

7. Study Schedule of Events and Visit Descriptions

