Per-protocol set (PPS): It is a subset of FAS. The subjects in this data set are more compliant to the protocol, meet the inclusion/exclusion criteria, participate in randomization, receive 2 doses of vaccine according to the requirements of the protocol, and have serum-testing results before and after immunization. The subjects in this data set are included in PPS set. Among them, subjects who meet the following conditions are not allowed to involve the PPS data set: (1) they do not meet the selection criteria and meet the exclusion criteria; (2) Those who fail to obtain follow up data and

information after vaccination; (3) Serious lack of information and data after randomization; (4) The subject received the wrong inoculation or incorrect dose; (5) Other investigators consider it needs to be excluded. For those whose vaccination time exceeds the window or whose blood collection time exceeds the window after exemption, the researcher, the sponsor and the statistician shall jointly agree on the exceeding window time before blindness.

(3) Safety analysis data set

Safety Analysis Data Set (SS): includes all subjects who receive vaccination after randomization.

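### The overall between-arm SAE test is worded with a window after the full course, whereas the SAE endpoint runs from the first dose

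*Protocol*

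**What the plan says.** The SAE endpoint is defined twice. Protocol 4.4.3 gives "The incidence of serious adverse events (SAE) from the first dose of vaccination to 12 months after the last dose of vaccination"; the synopsis, under Trial endpoint, gives "The incidence of serious adverse events (SAE) from the beginning of the first dose to 12 months after the whole course of immunization". Both start at dose 1.

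The test is also stated twice, in 9.3(5) and in the synopsis under Statistical Methods (5), with identical timing. A chi-squared or Fisher test is used to compare "the difference of SAE incidence rate between the experimental and placebo groups within 360 days after the whole inoculation". No start at dose 1 is mentioned in either place.

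Four other provisions bear on this:

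- Analysis set (9.2): "Safety Analysis Data Set (SS): includes all subjects who receive vaccination after randomization". Two doses are not required, and 9.3(5) is headed as an analysis of this set.
- Schedule (6.6): "The subjects will complete 2 doses of vaccine on D0, D21(+7) days".
- Bar to dose 2 (5.1.3) includes: "Serious adverse reactions with causal relationship with the previous dose of vaccine".
- The end of 9.3(5) adds a MedDRA-coded comparison of adverse events and SAEs at SOC and PT level, with no time window.

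**The concern.** The endpoint and the test meant to compare it between arms cover different periods. A window anchored on completing the course has no place for an SAE between the doses. It is also undefined for anyone who never completes the course.

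The second group is not a random sample. Under 5.1.3 a causally related serious reaction to dose 1 prevents dose 2, and 5.1.4 withdraws subjects for intolerable adverse events. A subject who dies between the doses also has no window. These are events that an overall SAE comparison in a vaccine trial is meant to capture. If one arm has more of them, the test as worded would not see the excess. Safety is a secondary objective, and choosing the window after unblinding would be a post hoc decision.

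**Working it through.** **Inputs.** Dose 2 on D21, window +7 days (6.6), so D21 to D28. Test window of 360 days after the full course (9.3(5)). Twelve-month visit after the full course at D381 (7.4.7 and Table 4). Planned arm size 15,000 (4.2).

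**Reproducing the plan's own timing.** 21 + 360 = 381, which matches the 12-month visit day. The protocol therefore treats 12 months as 360 days and counts them from dose 2.

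**Length of each window.**

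| | Dose 2 on D21 | Dose 2 on D28 |
|---|---|---|
| Endpoint, dose 1 to 360 days after dose 2 | 21 + 360 = 381 days | 28 + 360 = 388 days |
| Test, as worded | 360 days | 360 days |
| Left out | 21 days | 28 days |
| Share of endpoint period | 21/381 = 5.5% | 28/388 = 7.2% |

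**Which reading the text favours.** The clause just before the SAE test in 9.3(5) compares adverse reactions at 30 minutes, 0-7 days and 8-28 days after each dose. There the window plainly opens at the injection named. The SAE clause uses the same construction but changes the anchor from each dose to the whole course. With D381 = D21 + 360, a window opening at dose 2 is the natural reading.

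**Who has no window.** A subject given only dose 1 belongs to the Safety Set but has no date of completed inoculation. As worded, such a subject may stay in the denominator, but no SAE of theirs can fall inside the window.

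**Illustration of size (assumed rates; the protocol gives no SAE rate).** Expected SAEs per arm between the doses = 15,000 × annual rate × days/365.

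- 0.5% per year, 21 days: 15,000 × 0.005 × 21/365 = 4.3
- 1% per year: 8.6 (21 days) to 11.5 (28 days)
- 2% per year, 28 days: 15,000 × 0.02 × 28/365 = 23.0

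The omitted events are thus roughly 4 to 23 per arm at a constant risk.

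**Illustration of a difference confined to the interval between doses (assumed counts).** With 15,000 per arm, Fisher's exact test gives p = 0.031 for 6 against 0, p = 0.012 for 10 against 1, and p = 0.002 for 10 against 0. None of these events would enter the test as worded.

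**The case against.** The strongest reply is that the phrase "within 360 days after the whole inoculation" fixes only an end point. It resembles the end of the synopsis endpoint, whose start is dose 1. In a loosely worded text it could be shorthand for everything up to 360 days after the full course. That reading is possible, but the parallel clause on reactions points the other way. Even if it was the intention, a programmer following the sentence could leave out the events between doses, so the wording still needs correcting.

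Other objections stand and limit the point:

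- A reader might infer that one-dose subjects are dropped from the safety analysis. They are not: 9.2 keeps every vaccinated subject in the Safety Set. What is missing is their window in this one test.
- A reader might infer that this is the only between-arm comparison of SAEs. It is not: 9.3(5) also compares SAEs by SOC and PT. No window is stated there, so that comparison neither shares the problem nor clearly solves it.
- Reactions after dose 1 are compared separately, and all events are described and listed. A related serious reaction to dose 1 can therefore enter a between-arm test as a reaction. Those tests do not count SAEs as such, and an unrelated SAE would not enter them.
- Bias toward no difference is conditional. With the same SAE risk in all arms, losing 21 to 28 days costs some information and creates no bias.
- The number of subjects without a window cannot be derived. The 15% drop-off in 9.4.1 is an allowance in the efficacy sample size and says nothing about how many leave before dose 2.
- Safety oversight does not rest on this sentence. SAEs are reported within 24 hours (8.3), and the DSMB reviews AE and SAE data (8.5).

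**Conclusion.** The point holds as a contradiction within the protocol: the overall SAE test in 9.3(5) and the synopsis does not cover the period of the SAE endpoint in 4.4.3 and the synopsis. Read as written, it omits 21 to 28 days, or 5.5% to 7.2% of the endpoint period, and leaves one-dose subjects without a window. At a constant and equal risk the effect is small. It matters if serious events cluster after dose 1 in a vaccine arm, because the test would then understate the difference, and related serious reactions that bar dose 2 would not count in it at all.

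This rests on the literal reading of the window, on 12 months being 360 days as in the visit schedule, and on dose 2 being given on schedule. The SAE rates and counts above are assumptions and only show scale. The documents do not support the inference that safety data are lost or that an excess of SAEs would go unexamined.

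**What to change.** In 9.3(5) and in the synopsis under Statistical Methods (5), state the SAE comparison window as: from the first dose to 12 months after the last dose received, in all Safety Set subjects, including those who received only one dose. Anchoring on the last dose received gives one-dose subjects a defined end date; the synopsis endpoint, which ends relative to the whole course, should carry the same wording. A window after dose 2 may be kept as a supplementary analysis.

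The cost is one sentence in two places plus the aligned endpoint line. SAEs are already collected from the first dose, so no new data are needed, and no dosing or withdrawal rule changes. It should be done before unblinding.

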Dyspnea	Dyspnea during exercise	Normal activity dyspnea	Difficulty in breathing during rest	Dyspnea, need oxygen therapy, hospitalization or assisted breathing
Non-injection site pruritus (No skin damage)	Mild itching does not affect or slightly affects daily life.	Pruritus Affects Daily Life	Itching makes it impossible to carry out daily life.	NA
Abnormal skin and mucosa	Erythema/itching/color Change	Diffuse rash/maculopapule/dryness/desquamation	Blisters/exudations/desquamation/ulcers	Exfoliative dermatitis involves mucosa, or erythema polymorpha, or suspected Stevens-Johnsons syndrome
Acute allergic reaction**	Local urticaria (blisters) without treatment	Local urticaria, requiring treatment or mild angioedema, without treatment	Extensive urticaria or angioedema requiring treatment or mild bronchospasm	Anaphylactic shock or life-threatening bronchospasm or laryngeal edema
Fatigue	Does not affect daily activities	Affect normal daily activities	Seriously affecting daily activities and unable to work	Emergency or hospitalization

Note: * Axillary temperature is usually used in China, which is converted into tympanic temperature, oral temperature and anal temperature when necessary. Usually, tympanic temperature/temporal artery temperature = axillary temperature +0.5 °C. When persistent high fever occurs, the cause of high fever should be determined as soon as possible.

* For constipation, attention should be paid to the changes before and after vaccination.

For clinical abnormalities not covered in the above classification Table 3, the intensity classification evaluation of adverse reactions shall be carried out according to the following standards:

Grade 1	Grade 2	Grade 3	Grade 4	Grade 5
Mild: short-term (< 48h) or slight discomfort, does not affect activities, does not need treatment	Moderate: Mild or moderate movement restriction, may require medical treatment, no or only mild treatment is required.	Severe: obvious activity Restricted, need to see a doctor and receive treatment, may need to be hospitalized.	Critical: May threaten life, severely restricted activities, requiring monitoring and treatment	Death

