9.4. Sample size

9.4.1. Calculation of sample size for vaccine efficacy study

The sample size required for phase III in vaccine efficacy study should meet the following requirements: ① For trial vaccine-1 or trial vaccine-2, the point estimation value of any vaccine efficacy is over 50%; ② the lower limit of 95% CI of any vaccine efficacy of trial vaccine-1 or trial vaccine-2 is no less than 30%.

Assume VEs of both vaccine-1 and vaccine-2 could reach 0.6. If 95% CI of any one of the two vaccines' efficacy is larger than 0.3, the vaccine will be considered to be successful. The statistical power achieves 90% when the number of COVID-19 cases in any one vaccine and placebo groups is 150. There are vaccine-1 and vaccine-2 groups in this trial. It will be analyzed when the number of COVID-19 cases in any one vaccine and placebo groups achieves 150.

The sample size required for each vaccine group was calculated by reference to document ^[15] according to the confirmed cases' cumulative number of COVID 19 epidemic situation in UAE and several other research sites since Jan. 2020 and the trend of newly diagnosed cases per day most recently, assuming the annual incidence rate of placebo group, P1 is 850/100,000, and the ratio of trial vaccine -1, trial vaccine -2 and placebo control group is 1:1:1.

$$N2=T/[(C+1- \pi 1) \times P1]=150/[(1+1-0.6) \times 0.0085]=12605 \text{ cases}$$

In the above formula, $\pi 1$ is the point estimation of VE, and C is the sample proportion of the test group and the control group.

If the drop-off rate is estimated as 15%, a total of $12605/(1-0.15) \times 3=44488$ cases were needed in the three groups. Considering the per capita distribution in the multi-center study site, 45,000 cases were planned and 15,000 cases in each group and the samples cases were allocated according to features of each site.

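### The rank-sum test on reaction grades leaves its unit and the scoring of non-reactors open; on its natural reading it can miss, or with a large excess of mild reactions reverse, a higher rate of severe reactions

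*Protocol*

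**What the plan says.** Section 9.3(5), repeated in the synopsis, gives one sentence on severity: "The rank sum of two independent samples is used to compare the average grade of adverse reactions in the experimental and placebo groups". It names the test and the variable, but not the unit or the score for someone with no reaction.

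These parts of the protocol bear on how to read it:

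- **Analysis set.** The subsection is headed as an analysis of the safety set, which "includes all subjects who receive vaccination after randomization" (Section 9.2).
- **Grade scale.** In Section 4.7.2 the lowest category of Tables 2 and 3 and of the general scale is Grade 1. The general scale describes it as "Mild: short-term (< 48h) or slight discomfort, does not affect activities, does not need treatment". No category for no reaction is defined.
- **Repeats.** When a subject has the same reaction more than once, "the description on this adverse reactions/events should indicate the most severity". Different reactions in one subject are not addressed.
- **Companion tests.** Chi-square or Fisher tests compare "the incidence of total adverse reactions, systemic adverse reactions, local adverse reactions and unexpected adverse reactions in the experimental and placebo groups within 30 minutes" and in the later windows. SAE incidence is also compared, and Section 9.3 adds comparisons by SOC and PT. None is split by grade.
- **Grade 3 or higher.** This appears in Section 5.1.5 as a trigger for discussing suspension ("When the incidence of grade 3 and above adverse reactions reaches 15% or above"), not as a comparison between arms.

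**The concern.** A subject without a reaction has no grade on the protocol's scales, so a programmer following the sentence would rank grades among reactions, or among subjects with a reaction. Having a reaction is an outcome of vaccination. If a vaccine adds many grade 1 reactions, the average grade in that arm falls even when severe reactions per vaccinated subject rise.

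If the unit is the reaction, one subject can enter several times: Section 4.7.1 lists 6 local and 16 systemic solicited terms. A test for two independent samples would then treat correlated grades as independent and reject too often.

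What is at stake is the only between-arm comparison of reaction severity that the protocol states. Its result could read as no worse, or milder, while grade 3 or higher reactions are more frequent per subject.

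**Working it through.** **1. Plan's own figure.** The protocol gives none for this test. The one design input used is the arm size: "45,000 cases were planned and 15,000 cases in each group" (Section 9.4.1). It follows from the stated formula: 150/[(1 + 1 − 0.6) × 0.0085] = 12,605, and 12,605/0.85 × 3 = 44,488, rounded up to 45,000.

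**2. Assumptions.** The protocol gives no reaction rates or grade distribution, so every rate below is illustrative.

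**3. One worked example (15,000 per arm).** Assumed counts at grades 1/2/3/4 are vaccine 4700/1000/270/30 (6,000 reactors, 40%) and placebo 2100/750/135/15 (3,000 reactors, 20%). Grade 3 or higher is 300/15,000 = 2.0% against 150/15,000 = 1.0%. The rank-sum test estimates θ = P(vaccine grade higher) + ½P(tie); 0.5 means no difference.

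- Reactors only, with proportions 0.783/0.167/0.045/0.005 against 0.700/0.250/0.045/0.005: θ = 0.783 × 0.350 + 0.167 × 0.825 + 0.045 × 0.9725 + 0.005 × 0.9975 = 0.460. Tie-corrected z = −8.2: the vaccine looks milder.
- All subjects, none = 0, with proportions 0.600/0.313/0.067/0.018/0.002 against 0.800/0.140/0.050/0.009/0.001: θ = 0.597, z = +36.2: the vaccine is worse.
- If every grade simply doubles (4200/1500/270/30 against the same placebo counts), the reactors-only test gives z = 0, p = 1.0.

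**4. How often, and how it depends on the excess of reactors.** Simulated grade counts at 15,000 per arm, one grade per reactor, two-sided 5% rank-sum. Grade 3 is 1.5% against 1.0% in every row.

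| Placebo grades 1/2/3 (%) | Vaccine grades 1/2/3 (%) | Excess of reactors (points) | Reactors only: vaccine milder | Reactors only: vaccine worse |
|---|---|---|---|---|
| 35/4/1 | 49.5/4/1.5 | 15 | 99% | 0% |
| 20/4/1 | 33/5.5/1.5 | 15 | 85% | 0% |
| 21/3/1 | 34/4.5/1.5 | 15 | 26% | about 0% |
| 35/4/1 | 40/4/1.5 | 5.5 | 8% | about 1% |
| 20/4/1 | 28/5.5/1.5 | 10 | 2% | about 3% |
| 35/4/1 | 36.5/4/1.5 | 2 | about 0% | 22% |
| 35/4/1 | 35/4/1.5 | 0.5 | 0% | 50% |

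The reversal needs a large excess of mild reactions. With moderate excesses the test mostly finds nothing. With almost no excess it works in the right direction.

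**5. Direct comparison of grade 3 incidence per subject.** For 1.5% against 1.0%, expected z = 0.005/√(2 × 0.0125 × 0.9875/15,000) = 0.005/0.00128 = 3.9. Power is about Φ(3.9 − 1.96) = 97% in every row, whatever the excess of mild reactions.

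**6. Rank-sum with none = 0.** It finds the vaccine worse in 100% of trials in the first five rows. That mostly reflects incidence: in the last row, where only severity differs, it detects harm in about 22% of trials, against 50% for reactors only.

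**7. Several reactions per subject (reaction-level reading only).** With no true difference, 3,000 per arm, 40% with a reaction, a mean of 2 to 3 reactions per affected subject and within-subject correlation 0.2 to 0.6 (all assumed), the nominal 5% test rejected in about 7% to 17% of trials.

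**The case against.** A reader might infer that the protocol fixes a reactors-only test and that it will make the vaccines look milder. The documents support neither statement.

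- **Unit and scoring are open.** The safety set includes every vaccinated subject, so a subject-level score with zero for no reaction is possible. Section 9 defers details to a separate statistical analysis plan, which could settle this. That stands, and it limits the point to the wording and its natural reading. The zero-scored version does, however, need a category that the grading scales do not contain.
- **The rates are assumed.** The reversal appeared reliably only with a 15-point excess of reactors. The placebo contains the same adjuvant dose (Section 4.3), so a gap that large cannot be presumed. This stands.
- **Other tests give warning.** With a 15-point excess, the total-incidence test flags the vaccine in every simulated trial. The SAE comparison covers part of the severe end, since several Grade 4 definitions involve hospitalisation, and SOC and PT comparisons are stated too. A claim of no worse reactogenicity would sit beside contrary results. This stands, except that none of these tests separates severe from mild reactions.
- **No decision rests on it.** The safety endpoints are incidences, the suspension trigger uses grade 3 or higher incidence, and DSMB review is separate. This stands and lowers the severity.
- **A zero-scored rank-sum largely repeats the incidence tests.** This also stands, so the grade 3 or higher comparison is the useful part of the change.

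**Conclusion.** The point holds in a limited form. The severity test has no stated unit and no rule for non-reactors. Read naturally, it conditions on a post-vaccination outcome, and if reactions are the unit it also ignores clustering within subjects. Under assumed rates with grade 3 at 1.5% against 1.0% and 15,000 per arm, it called the vaccine milder in 26% to 99% of trials with a 15-point excess of reactors, and in under 10% with 5.5 to 10 points. The more general weakness is that it can miss the difference: in those five scenarios it found the vaccine worse in at most about 3% of trials, while grade 3 incidence per subject did so in about 97%. All of these figures rest on assumed rates and on the reactors-only reading. Severity is low, because this is a secondary safety analysis with no decision rule attached.

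**What to change.** In Section 9.3(5) and the synopsis, replace the sentence with a between-arm severity comparison of this kind: for each dose, each vaccine is compared with placebo on the proportion of safety-set subjects with at least one adverse reaction of grade 3 or higher, by chi-square or Fisher's exact test. If a rank-sum test is kept, apply it to each safety-set subject's highest grade, with 0 for no reaction, and show grades among reactors descriptively only.

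The cost is wording in two places. Grades and the safety-set denominator are already collected. There are two downsides. A subject-level maximum does not show how many reactions a subject had, although the listing of all reactions does. The zero-scored rank-sum mostly reflects incidence, so it should not stand as the severity result on its own.
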